Every admitted patient will be included for evaluation of the primary and secondary outcomes (a-e + j-k) regardless of the patient's cognitive status. However, the remaining secondary outcomes (f-i) will require that the patient is able to understand the Danish language and cognitively able to answer the questions meaningfully. A dedicated project nurse will assist during the hospital admission if required. A patient can be included several times due to recurrent dislocations which will be accounted for during statistical analysis.

Outcome/variable time table

Pre-admission (recall past 14 days)	Hospital ad- mission (Day 0)	Day 1	Day 3	Day 7	Day 14	Day 30	Day 90	Day 180	Day 365
Patient-reported outcomes									
NRS	NRS	NRS	NRS	NRS	NRS	NRS			
HOOS					HOOS		HOOS	HOOS	HOOS
EQ-5D					EQ-5D		EQ-5D	EQ-5D	EQ-5D
	Satisfaction								
Registry/Patient file outcomes									
	Time to reduction								
	Time to discharge								
	Per-operative Complications								
	Post-operative complications								
						Re- admissions			
						Mortality	Mortality		
Patient variables									
	Age								
	Sex								
	ASA-score								
	BMI								
	Specific comorbidities								
Prosthesis variables									
	Primary operation date								
	No. of previous dislocations								
	Type of prosthesis (incl. liner type)								

Information acquired from patient files: Information regarding patient-related factors (age, sex, ASA-score, BMI, and specific comorbidities) and prosthesis-related factors (primary operation date, number of previous dislocations, and type of prosthesis), as well as information regarding

30-days readmission and mortality, and 90-days mortality will be acquired from the patient files after acquired patient consent. The patient- and prosthesis-related factors will be used to control for potential confounding. The acquired patient file information is dated from admission to 90 days post-admission. The prosthesis-related information is dated to the primary operation date. We will only access patient files from patients who accept to participate, therefore 120 patients.

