As the acute treatment has been performed when the patient is asked for consent, we apply for the use of the data acquired during the acute treatment of the patient, regardless of whether they choose to participate in the secondary part of the study regarding the patient-reported outcomes, in order to not prolong the study unnecessary. This includes the patient- and prosthesis-related factors, as this will be used to control for potential residual confounding.

Sample size

Study sample size are based on the primary outcome “Time from arrival at the emergency entrance to prosthesis reduction”, applying a formula for RCT studies with clinically superiority design (21). The null-hypothesis dictates no difference in time from arrival at the emergency entrance to prosthesis reduction for patients following the Standard Pathway or the Fast-Track Pathway.

$$N = 2 \times \left(\frac{z_{1-\alpha} + z_{1-\beta}}{\delta - \delta_0} \right)^2 \times s^2$$

N = no. of patients in each group

Alpha-value = 0,05 (5% risk of type-1 error)

Beta-value = 0,90 (10% risk of type-2 error)

Delta-value (estimated true value between the two groups) \approx 4 hours

Delta₀-value (estimated clinical acceptable difference between the two groups) \approx 3 hours

S-value (pooled standard deviation (SD) for both groups) \approx 2.5 hours

A review of 16 randomly selected patients that was admitted to the University of Southern Denmark, Esbjerg, with a dislocated THA from January 2018 to May 2022 revealed a mean time from arrival at the emergency entrance to prosthesis reduction at 6 hours (range 2.7 – 9.0 hours) with a standard deviation at 1.6 hours.

$$N = 2 \times \left(\frac{1,645 \times 1,28}{4 - 3} \right)^2 \times 2,5^2 \approx 53 \text{ patients in each group}$$

Based on a review of the surgical procedures performed during the period 01.02 – 31.08.2022, we expect to admit 5-6 patients per month with a dislocated THA or HA, and we expect an attendance rate of >90% based on the primary outcome. Therefore, we will include 53 patients + 15% ≈ 60 patients in each group, due to the risk that specific comorbidities will lead to exclusion from the Fast-Track pathway by the anesthetic staff. It is thus expected that a total of 120 patients will be adhered to one of the two treatment algorithms over the course of 24 months.

Blinding

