The patients are informed that consent gives the trial manager, sponsor and sponsor's representatives as well as any supervisory authority direct access to obtain information in the patient's medical record, etc., including electronic medical records, in order to see information about the subject's health, which is necessary as part of the implementation of the research project and for control purposes, including self-control, quality control and monitoring, which they are obliged to carry out.

Statistics

Mean values with standard deviation (SD) are given for normally distributed data, while median values with interquartile range (IQR) are given for skewed data. In case of normally distributed data, two-sample t-test is used. Mann-Whitney U-test is used to compare continuous nonparametric variables and chi-square test is used to compare categorical variables. STATA version 18 will be used for all statistical analyses.

Economy

The main investigator and initiator is [name], Ph.D., post.doc.

The study is conducted as a collaboration between the Department of Orthopedics, Department of Anesthesiology, Department of Radiology, and Department of Emergency Medicine, University Hospital of Southern Denmark, Esbjerg. There are no special economics involved in the study between the departments, as the study is carried out as a part of normal daily, acute activity.

Vestjysk Orthopedic Fund will be applied for covering expenses to hardware (computer, Ipad etc.)

The Region of Southern Denmark's Research Fund will be applied for covering salary to a dedicated study nurse.

Grants are administered via an account that is subject to public audit.

There are no conflicts of interest.

Ethics

Permission to store and handle data is obtained upon application to the Region of Southern Denmark's internal register (24/34681). The Danish Law of data protection is observed.

The regional ethics committee has been applied for permission to conduct the study under special circumstances as acute research without the possibility of obtaining informed consent from the

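### The tests stated in Statistics cannot deliver the promised confounding control or, without a one-admission-per-patient rule, account for repeat inclusions

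*Protocol*

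**What the plan says.** Only the Protocol is at hand. Under Trial design it describes an observational cohort. Under Setting, first-year patients follow the standard pathway and those admitted after 1 September 2025 follow Fast-track. The paragraph on X-ray dose speaks of randomisation, but no random mechanism is described anywhere.

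The Protocol makes two commitments about the analysis:

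- **Repeat inclusions (Outcomes).** "A patient can be included several times due to recurrent dislocations which will be accounted for during statistical analysis". Participants excludes recurrences only within one admission, so later readmissions do enter the data.
- **Confounding (Information acquired from patient files).** "The patient- and prosthesis-related factors will be used to control for potential confounding". The factors are age, sex, ASA score, BMI, comorbidities, date of the primary operation, previous dislocations and prosthesis type. The purpose is repeated just before Sample size: "This includes the patient- and prosthesis-related factors, as this will be used to control for potential residual confounding".

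Statistics names these tests: "In case of normally distributed data, two-sample t-test is used. Mann-Whitney U-test is used to compare continuous nonparametric variables and chi-square test" for categorical variables. Otherwise it gives only summary measures and the software. It mentions no regression, stratification, matching, weighting, clustering method or one-admission rule.

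The text is divided on access to the factors. One paragraph says "We will only access patient files from patients who accept to participate, therefore 120 patients". The next seeks the acute-treatment data, these factors included, "regardless of whether they choose to participate in the secondary part of the study regarding the patient-reported outcomes".

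**The concern.** In a comparison of one year with the next, any difference in case mix between the years is part of the crude difference in time to reduction. That is presumably why the factors are collected. The named tests compare two sets of values and have no place for a covariate, so the factors have no route into the result.

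The tests also assume independent records. If a patient contributes several admissions and outcomes are correlated within patients, the standard error is wrong. It is mainly too small when the repeats fall in the same year. In a per-admission chi-square test of 90-day mortality, a patient admitted twice within 90 days who then dies can count as two deaths.

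At stake are the estimated difference, its confidence interval and the secondary comparisons, which have no large assumed effect to protect them.

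**Working it through.** The Protocol gives no figure on this point to reproduce. The check is a comparison of texts, followed by illustrations of size.

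**1. Commitments against stated tests**

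| Commitment | t-test, Mann-Whitney, chi-square |
|---|---|
| Control confounding with listed factors | Not possible: no covariates enter |
| Account for repeat inclusions | Only if reduced to one admission per patient, which is not stated |

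A one-admission rule would meet the second commitment but not the first.

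**2. Scale.** Sample size gives SD 2.5 h, 60 per group and an expected difference of 4 h. The derivation of the sample size is a separate matter and nothing here depends on it.

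SE = 2.5 × √(2/60) = 0.456 h, and 4 / 0.456 = 8.8 standard errors.

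**3. Repeat admissions (all inputs assumed).** Simulation with no true effect, 60 admissions per year and 10,000 replicates per setting (Monte Carlo SE 0.2 to 0.3 points). Patients have 1, 2, 3 or 4 admissions with probability 0.75, 0.15, 0.07 or 0.03. Each repeat falls in the other year with the probability shown. ICC is the within-patient correlation. Type I error of the nominal 5% t-test:

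| ICC | 0% cross | 25% cross | 50% cross |
|---|---|---|---|
| 0.05 | 5.8% | 5.3% | 5.2% |
| 0.1 | 6.0% | 5.4% | 4.9% |
| 0.2 | 7.2% | 5.7% | 5.2% |
| 0.5 | 9.7% | 7.1% | 5.0% |

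Over the same 12 settings, patient-clustered standard errors gave 5.0% to 5.6% and first admissions only gave 4.7% to 5.4%. A separate simulation (8,000 runs, on average 1.25 to 1.5 admissions per patient, all in one year, ICC 0.3 to 0.5) gave 6.7% to 10.6%, against 5.1% without repeats.

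**4. Confounding (inputs assumed).** Bias = difference between years in the share of a patient type × extra waiting time for that type.

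- Low: 0.05 × 0.5 h = 0.025 h, or 0.025 / 0.456 = 0.05 SE. Coverage of the 95% CI is 95.0%.
- High: 0.20 × 2 h = 0.40 h, or 0.40 / 0.456 = 0.88 SE. Coverage is Φ(1.96 − 0.876) − Φ(−1.96 − 0.876) = 85.8%.

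**5. Deaths counted per admission (inputs assumed).** Same repeat pattern with all repeats in one year, and 90-day mortality of 5% or 10% per patient. With gaps between admissions of up to 90 days, the chi-square error is 7.1% or 8.6%. With gaps of up to 365 days it is 4.8% or 5.5%. For independent records at the same event rates it is 4.2% to 5.0%.

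**The case against.** The strongest reply is that Statistics is a short list of default tests and is not called exclusive. The commitments to adjust and to account for repeats stand elsewhere, and a statistical analysis plan may supply the model. That stands as far as detail goes: the exact model, the handling of skewed times and the models for repeated questionnaires can be left to such a plan, and their absence is no finding. It does not remove the mismatch. The section that states the tests names none that can do what the Protocol commits to, so a plan that honours the commitments must go beyond it.

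The second reply concerns size. Time to reduction on the standard pathway depends largely on logistics such as staff availability, theatre activity and fasting, which argues for a low within-patient correlation. The two years are consecutive, at one hospital, with the same listed criteria. With 60 per group, a factor of 50% prevalence differs by chance with a standard error of √(2 × 0.5 × 0.5 / 60) = 9 points. A 5-point difference is therefore ordinary sampling variation, which the t-test's standard error already covers; only systematic drift is bias. All this stands, and the effect may be small.

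Three stronger readings are tempting, and the documents do not support them:

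- **A failed 3 h margin test.** Sample size uses 3 h as the "estimated clinical acceptable difference between the two groups". A reader might infer that confounding inflates the error of a test against it: with 0.40 h bias, the one-sided error at a true 3 h difference would be P(Z > 1.645 − 0.876) = 22%. But the stated null hypothesis is no difference, and no test against 3 h is planned.
- **First admissions only would leave too few patients.** Under the repeat pattern assumed above, about 88 of 120 admissions remain, or 44 per year, below the planned 53. This treats 60 as admissions. Sample size speaks of patients; if these are distinct people, 60 per year remain.
- **The main conclusion is unsafe.** At 8.8 standard errors, rejection of no difference does not depend on these points if the true effect is 4 h.

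**Conclusion.** The point holds as a mismatch between the stated tests and the Protocol's own commitments, in a non-randomised comparison where adjustment matters. It should be corrected.

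If the tests are applied to all admissions, case-mix differences stay in the estimate and its confidence interval. Standard errors may be misstated, and are too small mainly when repeats fall within one year and within-patient correlation is appreciable. One death may be counted at two admissions.

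The size cannot be known from the documents. The illustrations run from negligible, with low correlation or much crossing between years, to a type I error near 10% and a shift of 0.40 h at the unfavourable end. Confidence is high in the mismatch and low in any particular size.

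**What to change.** In Statistics:

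- Make the primary analysis a regression of time to reduction on pathway, adjusted for a pre-specified set of the listed patient and prosthesis factors, with patient-clustered standard errors. Report the adjusted difference with its confidence interval.
- Count each death once per patient.
- Keep the t-test, Mann-Whitney and chi-square as crude comparisons or as first-admission-only sensitivity analyses.
- State what adjustment does not remove: calendar trends, and selective loss from one arm. Sample size itself adds patients "due to the risk that specific comorbidities will lead to exclusion from the Fast-Track pathway by the anesthetic staff".

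In Information acquired from patient files, reconcile the two statements on whether the factors may be used for patients who decline the second part. The adjusted model depends on the answer, so settle this first.

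The cost is wording and slightly more analysis in the software already named. Confidence intervals may widen. If the factors are unavailable for patients who decline, a complete-case adjusted model loses their records. If first admissions only are used and 60 means admissions, the standard error under the repeat pattern assumed above rises from 0.46 h to 2.5 × √(2/44) = 0.53 h, which is a reason to keep that analysis as a sensitivity analysis.

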The dislocated prosthesis is usually managed by a simple, closed reduction maneuver under general anesthesia with or without muscle relaxation, resulting in open surgical reduction rarely being needed (9-11). Time from admission to actual reduction often includes various steps (incl. several patient transfers between emergency units, radiology departments, operating theaters) which causes an unnecessarily long period of pain for the patient. In 2015, a fast-track system was introduced at Hvidovre Hospital on a trial basis for patients highly suspected for THA/HA dislocation (12). This resulted in a significant decrease in the time from arrival to reduction and overall time of hospitalization, without resulting in more complications. The study was retrospective and did not measure how patients experienced the change in practice.

A fast-track system must be specially designed for the local departments, due to differences in the logistical options from hospital to hospital. The purpose of this study is to design a fast-track pathway for patients referred to the University Hospital of Southern Denmark, Esbjerg, with high probability of having a dislocated hip prosthesis with the primary aim to reduce the time from arrival to reduction and the total hospitalization time. Secondary aims are to

- investigate whether quicker prosthesis reduction influences on hip function and quality of life afterwards
- reduce the pain experience immediately and in the long term
- increase patient satisfaction

without changing the overall complication rate and readmission/mortality

Methods:

Trial design

The study is designed as a prospective observational cohort trial, adhering to the STROBE guidelines (13). The present protocol will be registered at clinicaltrials.org and submitted for publication in an international journal.

Setting

The study is conducted at the University Hospital of Southern Denmark, Esbjerg, as a collaboration between the Department of Orthopedics, Department of Anesthesiology, Department of Radiology, and Department of Emergency.

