The goal for the new fast-track sedation pathway is a short deep sedation, according to the definition of level of sedation by ASA (14). This is for optimal patient comfort and success and with very low risk of aspiration (15, 16). The patient is sedated with Propofol 0,5-1 mg/kg and/or Esketamine 0,1-0,5 mg/kg. If a repeat dose is necessary, it is with Propofol 0,2 mg/kg and/or Esketamine 0,1-0,5 mg/kg (17, 18). Before sedation an intravenous line is placed with 1 L Ringer Acetate and the patient will receive a nasal cannula with an oxygen flow of 2-5 L/min. During the sedation the patient is monitored with a non-invasive blood pressure, saturation, respiratory rate, pulse and 3-point ECG and the nurse anesthetist and anesthesiologist will continuously observe the depth of sedation and respiratory drive. After the hip reduction, the patient is observed and monitored until the sedation has worn off and there is no risk of airway obstruction.

Outcomes

The *primary* outcome is time from arrival at the emergency entrance to prosthesis reduction.

The *secondary* outcomes are:

- a) total hospitalization time from arrival to discharge
- b) intra-operative complications (fracture, unsuccessful reduction, aspiration, need for mask ventilation and/or intubation, others)
- c) post-operative complications (cardiac, pulmonal, thrombo-embolic events, nerve damage, re-dislocation, others) during hospitalization
- d) 30 days re-admission
- e) 30- and 90-days mortality
- f) hip-related pain measured by a 10-digit numeric rating scale (NRS)
- g) patient-reported outcome (PRO) using the Hip disability and Osteoarthritis Outcome Score (HOOS), domains ¹⁾PAIN, ²⁾OTHER SYMPTOMS, ³⁾FUNCTION IN DAILY LIVING, AND ⁴⁾HIP-RELATED QUALITY OF LIFE (19)
- h) Health-related quality of life using the EQ-5D questionnaire (20)
- i) patient satisfaction
- j) time consumption by the involved staff (orthopedic, anesthetic, radiology staff etc.)
- k) total hospital costs during admission

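### Pain, HOOS and EQ-5D are scheduled as repeated measures, but the tests named compare one value per patient and no principal comparison is fixed

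*Protocol*

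**What the plan says.** One of the secondary aims in the Background is to "investigate whether quicker prosthesis reduction influences on hip function and quality of life afterwards"; another is to reduce pain both at once and in the longer term. The Outcomes section supports these aims with NRS pain (item f), four HOOS domains (item g) and EQ-5D (item h).

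The outcome/variable time table schedules:

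- NRS at pre-admission recall and Days 0, 1, 3, 7, 14 and 30 ("NRS NRS NRS NRS NRS NRS NRS");
- HOOS and EQ-5D at pre-admission recall and Days 14, 90, 180 and 365 ("HOOS HOOS HOOS HOOS HOOS" for HOOS).

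The Statistics section matches tests to data type. For continuous data it says "two-sample t-test is used. Mann-Whitney U-test is used to compare continuous nonparametric variables", the first of these for normally distributed data; a chi-square test is named for categorical variables. It names no longitudinal model, no summary over time, no main time point and no use of the pre-admission score.

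Two sentences in the Outcomes section come close. One says repeat inclusions of a patient through recurrent dislocation will be accounted for. The other says patient and prosthesis factors will be used to control confounding. Neither concerns repeated questionnaires within one episode, and neither is given a method in the Statistics section.

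**The concern.** The protocol does not simply postpone its analysis. It names its tests for continuous data, and those tests do not match the repeated-measures schedule it sets out. Three things follow.

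1. **No principal comparison.** If each score is tested, many p-values arise for two aims, and nothing says in advance which of them carries the conclusion.
2. **Unused information.** A pre-admission score is collected for every scale but has no place in a two-sample test. Evidence from several follow-ups on the same scale is never combined.
3. **Missed visits.** Follow-up runs to Day 365. A test at one visit drops patients without a score there, even if their other scores are available.

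Patient-reported data are also the scarcer part of this study, because some patients cannot answer questionnaires.

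**Working it through.** The protocol gives no test count, power or error rate for NRS, HOOS or EQ-5D, so there is no stated figure to reproduce. Its one computed design figure, 53 per group, concerns the primary outcome and plays no part here.

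**Step 1. Count of scores** (time table; domains from Outcomes item g; one EQ-5D score per visit assumed)

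- NRS: Days 0, 1, 3, 7, 14, 30 = 6
- HOOS: 4 domains × 4 follow-ups = 16
- EQ-5D: 4 follow-ups = 4
- Total: 6 + 16 + 4 = 26

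The 26 are scores, not visits; there are nine occasions from Day 0. Patients are recruited for questionnaires after reduction, so the Day 0 NRS is most naturally post-reduction, but the table does not say so. Without it the count is 25.

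**Step 2. Chance of at least one p<0.05 with no true effect** (two-sided 0.05 per test is assumed; the protocol gives alpha for the primary outcome only)

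Independent tests: 1 − 0.95^26 = 0.736; for 25 tests, 1 − 0.95^25 = 0.723. Expected number of false positives: 26 × 0.05 = 1.3.

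Scores from the same patients are correlated. With a common correlation ρ between the 26 test statistics (assumed):

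| ρ | Chance of at least one |
|---|---|
| 0 | 74% |
| 0.3 | 62% |
| 0.5 | 48% |
| 0.7 | 32% |

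A structured version, with correlation over time 0.3 to 0.7 and between scales 0.4 to 0.8 (also assumed), gives 36% to 66%.

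One contrast per scale leaves six tests: 1 − 0.95^6 = 26% if independent, 21% at ρ = 0.5.

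**Step 3. Precision**

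Relative to one unadjusted score (variance 1), with common correlation ρ between all scores on a scale, including the pre-admission one:

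- one score adjusted for the pre-admission score: 1 − ρ²
- mean of k follow-ups: (1 + (k − 1)ρ)/k
- the same mean, adjusted: (1 + (k − 1)ρ)/k − ρ²

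| ρ | one score, adjusted | mean of 4 | mean of 4, adjusted |
|---|---|---|---|
| 0.3 | 0.910 | 0.475 | 0.385 |
| 0.5 | 0.750 | 0.625 | 0.375 |
| 0.7 | 0.510 | 0.775 | 0.285 |

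**Step 4. What this means for power**

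The Patient information section puts cognitive impairment at up to 15-20%. Of 60 per group, 60 × 0.80 = 48 to 60 × 0.85 = 51 remain, before refusals and loss to follow-up. Take 48 per group, ρ = 0.5 and an assumed effect of 0.4 SD that is constant over time:

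- one unadjusted score: SE = √(2/48) = 0.204 SD, 0.4/0.204 = 1.96, power 50%
- one adjusted score: SE = √(0.75 × 2/48) = 0.177, power 62%
- adjusted mean of four: SE = √(0.375 × 2/48) = 0.125, power 89%

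**Step 5. When averaging loses**

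For six NRS scores at ρ = 0.5, the mean has SE factor √((1 + 5 × 0.5)/6) = 0.764. If the effect is present at only m of the six points, the signal-to-noise ratio relative to a single test at an affected point is (m/6)/0.764: 0.22 for m = 1, 0.44 for m = 2, 0.87 for m = 4 and 1.09 for m = 5. Averaging over Day 0-30 therefore gains only if about five of the six points share the effect.

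**The case against.** **The analysis plan may settle this.** A lead time point, multiplicity handling and a longitudinal model for secondary outcomes are often left to a statistical analysis plan, which is not at hand. The Statistics section is short and generic, and is visibly not complete, since it gives no method for the confounder control promised elsewhere. This has weight against any complaint of missing detail. It does not remove the mismatch between the tests the protocol does name and the schedule it sets.

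**Nowhere does the protocol say that every time point will be tested.** This stands. A reader might infer 26 planned tests; that is an inference from the named methods and the absence of any summary measure, not a stated plan. Nor is there a success rule for secondary outcomes, so the text does not show that an aim would be declared met on whichever time point fell below 5%. The section on presentation of results commits to publishing negative and inconclusive findings too.

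**A chance finding is not clearly likely.** This also stands. The 74% needs independence between scores from the same patients; at correlations of 0.5 and 0.7 the figure is below one half.

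**The tests are not invalid.** Correct. A two-group comparison at one visit uses one value per patient, so correlation across visits does not bias it. A reader might conclude that repeated measurement breaks these tests; the loss is one of efficiency.

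**Averaging may hide what the trial seeks.** The expected benefit is a shorter period in pain, and Step 5 shows that a Day 0-30 mean can dilute an early effect. This stands and limits what should be prescribed for NRS.

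**Conclusion.** The concern holds as a poorly matched analysis choice for secondary outcomes f to h. Applied as written, the named tests ignore the pre-admission scores, discard patients who miss a given visit and leave 26 (or 25) scores without a principal comparison. The chance of at least one false positive if all are tested is about one third to three quarters. That range rests on assumed correlations and on a two-sided 5% level per test.

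The efficiency loss can be material: at ρ = 0.5 an adjusted mean of four follow-ups has 0.375 of the variance of a single unadjusted score. This assumes a fairly steady effect and a pre-admission score that correlates with follow-up as strongly as follow-ups do with each other. A 14-day recall may correlate less.

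The comparison of time from arrival to reduction is unaffected. The change is advisable; the study's main conclusion does not depend on it.

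**What to change.** In the Statistics section, replace the two-sample tests for NRS, each HOOS domain and EQ-5D with one linear mixed model per scale over the scheduled follow-ups. Terms: pathway, time, pathway-by-time, the recalled pre-admission score, the patient and prosthesis factors already listed for confounder control, and a patient-level random effect that also covers repeat episodes of the same patient.

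Fix one principal contrast per scale before outcome data are examined:

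- HOOS domains and EQ-5D: the overall pathway contrast over Day 14-365.
- NRS: a contrast the investigators choose in advance to match their aim on immediate and longer-term pain. An average over Day 0-30 should not be the automatic choice. State whether the Day 0 score is taken before or after reduction.

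Report all other time points as estimates with intervals. Six principal contrasts still carry a 21% to 26% chance of at least one false positive (ρ = 0.5 to independence), so the report should say that they are six.

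The cost is wording only: no new data, visits or patients. The downside is that non-principal time points become descriptive, and the overall contrast loses its precision advantage if the effect is confined to a few visits.

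### If hospital costs and staff time are judged skewed, the plan compares them by median and Mann-Whitney, which does not estimate the mean, and hence total, resource use

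*Protocol*

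**What the plan says.** The Outcomes section of the protocol lists "time consumption by the involved staff" as secondary outcome j and "total hospital costs during admission" as secondary outcome k. Both are to be evaluated in every admitted patient.

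The Statistics section holds a single rule for continuous data, with two branches:

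- Normal data: mean and SD. "In case of normally distributed data, two-sample t-test is used".
- Other data: "median values with interquartile range (IQR) are given for skewed data", and "Mann-Whitney U-test is used to compare continuous nonparametric variables".

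No separate rule is given for j or k. Among the assumed advantages of Fast-track, the Intervention section says that fewer patient transfers save time and hospital resources. The Outcomes section also foresees events that could make an admission expensive: "fracture, unsuccessful reduction, aspiration, need for mask ventilation and/or intubation, others". It gives neither a rate nor a cost for them.

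**The concern.** A statement about resources concerns the total used by a pathway, which is the mean per admission times the number of admissions. A median cannot be scaled up to a total. Mann-Whitney asks whether values in one group tend to rank above those in the other. Once an admission lies above all others, its rank is the same whether it cost twice or ten times as much, so the admissions that weigh most on a budget carry little extra weight in the test.

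The choice of branch adds to this. A small number of very costly admissions is what makes the data skewed, and skewness is what moves the analysis away from means. The mean therefore drops out in the situation where it differs most from the median.

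At stake is the reading of outcomes j and k: a saving could be reported at the wrong size or, in the less favourable case, in the wrong direction.

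**Working it through.** The protocol states no figure for j or k that could be reproduced. The check is therefore a reading of the rule, one worked example and one simulation. Only the group size comes from the protocol (60 per group, Sample size section). **Every cost and failure input below is an assumption.**

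**1. Worked example.** Standard: 60 admissions at 100. Fast-track: 54 at 80 and 6 failed reductions at 330.

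- Mean, Fast-track: (54 × 80 + 6 × 330) / 60 = 6300 / 60 = 105, against 100. Fast-track costs 5% more per admission.
- Median: 80 against 100. Fast-track looks 20% cheaper.
- Probability that a Standard admission costs more than a Fast-track one: 54 / 60 = 0.90. Mann-Whitney p is about 1 × 10⁻¹⁷, in favour of Fast-track.

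**2. When the true means reverse.** Let routine Standard cost be log-normal with median 1 and log-SD 0.3, so its mean is exp(0.3² / 2) = 1.046. Let routine Fast-track cost be 20% lower, a mean saving of 0.2 × 1.046 = 0.209. If a failed reduction adds c units in both pathways, with failure rates p_F (Fast-track) and p_S (Standard), then

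mean difference (Fast-track minus Standard) = −0.209 + (p_F − p_S) × c.

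The true mean is higher with Fast-track only if (p_F − p_S) × c exceeds 0.209. With 10% failures in Fast-track only, that needs c above 0.209 / 0.10 = 2.09 usual costs. With 5%, it needs c above 0.209 / 0.05 = 4.18.

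**3. Simulation of the same model**, 60 per group, two-sided 5% Mann-Whitney. A reversal is a significant Mann-Whitney result with a lower Fast-track median but a higher observed Fast-track mean.

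| Failures, Fast-track / Standard | Extra cost of a failure | True mean difference | Share of trials with reversal |
|---|---|---|---|
| 10% / 0% | 3 | −0.209 + 0.300 = +0.091 | about 44% to 47% |
| 5% / 0% | 3 | −0.209 + 0.150 = −0.059 | about 17% to 19% |
| 10% / 0% | 2 | −0.209 + 0.200 = −0.009 | about 17% to 19% |
| 10% / 5% | 3 | −0.209 + 0.150 = −0.059 | about 19% |
| 10% / 10% | 3 | −0.209 | about 5% |
| 10% / 0% | 1 | −0.209 + 0.100 = −0.109 | about 0% |

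Ranges show the spread between repeated runs. In the first row the median difference averages −0.17 while the mean difference averages +0.09, and Mann-Whitney is significant in about 70% of trials.

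Only the first row has a true reversal. In the others the true mean and the median agree in direction, and a reversal reflects chance in the observed mean. Even so, the size can be badly misread: with 5% failures in Fast-track only and an extra cost of 3, the median difference averages −0.18 while the mean difference is −0.06, a third of that.

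**The case against.** The rule is conditional. It never names j or k, and if their data look normal the t-test on means applies. A reader might infer that costs and staff time will certainly be compared by Mann-Whitney. The protocol does not support that, since it gives no distribution for either, and staff time for a short, standardised procedure need not be strongly skewed. This objection stands, and it is why the point is worded with an if.

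A reader might also infer that the plan is likely to declare Fast-track cheaper when it is dearer. That is not supported either. The scenario with the highest reversal share in the table places all failures in Fast-track, whereas the protocol counts complications in both pathways and its Ethics section sees no reason to expect greater risk with Fast-track. With equal failure rates the reversal share is about 5%. The opposite error, missing a true mean saving, has not been quantified here and is not claimed.

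It can further be said that a cost analysis belongs in a later analysis plan, that the Statistics section is short and generic, and that saving resources is offered as a rationale and not as a planned test. Unit costs, perspective and similar detail may indeed come later and are not criticised. But the Statistics section does more than stay silent: it sets a summary and a test for all skewed continuous outcomes, and those do not estimate mean resource use. Cost is the last of eleven secondary outcomes and is absent from the stated aims, which limits the weight of the point without removing it.

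**Conclusion.** The concern holds in conditional form. If j and k are judged skewed, the written rule leads to medians and Mann-Whitney, and neither gives the mean or total resource use. This follows from the protocol text and needs no assumption about costs.

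How far the result could mislead cannot be determined from the protocol. Under the assumptions shown, the share of trials pointing the wrong way on the observed mean runs from about 0% to 47%, depending on how common and how costly failures are and whether they occur in one pathway or both. Reversal is a possibility, not a forecast. The primary outcome is not affected, and the change is a desirable refinement for low-order secondary outcomes.

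**What to change.** Add one sentence to the Statistics section: for outcomes j and k, whatever the skewness, report arithmetic means by pathway and the mean difference with a bootstrap 95% confidence interval (for example bias-corrected), and give median and interquartile range as description only. The resampling unit should be the patient with all of that patient's admissions, because the protocol allows a patient to be included several times.

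The cost is one sentence and a bootstrap command. It needs no new data and no change in sample size. The downside is a somewhat wider interval when a few admissions are very costly. Writing the rule in advance also means that the cost measure is not chosen after the distribution has been seen.
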